# 5 Analysis Sets

For purposes of analysis, the following populations are defined in Table 2. Subjects to be included in the analysis sets will be done prior to breaking the blind.

Population	Description		
Enrolled Set	The Enrolled Set will include all participants who sign the ICF.		
Randomized Set	The Randomized Set will include all subjects who signed the ICF and were subsequently randomized into the study, regardless of study treatment administration.		
Full Analysis Set (FAS)	The Full Analysis Set will serve as the primary population for the analysis of efficacy and will consist of all randomized subjects who took at least 1 dose of double-blind study treatment and have at least 1 evaluable change from baseline in plasma desmosine / isodesmosine levels. Subjects will be analysed according to randomized treatment.		
Per-Protocol Set (PPS)	
 
The Per-Protocol Set includes all participants from the Full Analysis Set who have been treated according to the protocol and fulfil the following criteria: 
 
All inclusion/exclusion criteria satisfied
 
Absence of major protocol violations with respect to factors likely to affect the efficacy of treatment where the nature of protocol violation will be defined before breaking the blind
 
Adequate study medication compliance – to be determined before breaking the blind.
 
 
 
Subjects will be analysed according to randomized treatment.
 
		
Safety Set (SAF)	All randomized participants who take at least 1 dose of study treatment. Participants will be analysed according to treatment taken.		
PK Set (PKS)	The PK Set will include all participants in the Safety Set who have at least 1 evaluable serum concentration.		

Table 2: Definition of Analysis Sets

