### 10.2. Populations for Analyses

For purposes of analysis, the following populations are defined:

Population	Description
Enrolled Set	The Enrolled Set will include all participants who sign the ICF.
Randomized Set	The Randomized Set will include all subjects who signed the ICF and were subsequently randomized into the study, regardless of study treatment administration.
Full Analysis Set	The Full Analysis Set will serve as the primary population for the analysis of efficacy and will consist of all randomized subjects who took at least 1 dose of double-blind study treatment and have at least 1 evaluable change from baseline in plasma desmosine/isodesmosine levels. Subjects will be analyzed according to randomized treatment.

Population	Description
Per-Protocol Set	The Per-Protocol Set includes all participants from the Full Analysis Set who have been treated according to the protocol and fulfil the following criteria: 
 
1. All inclusion/exclusion criteria satisfied
 
2. Absence of relevant protocol violations with respect to factors likely to affect the efficacy of treatment where the nature of protocol violation will be defined before breaking the blind
 
3. Adequate study medication compliance, which will be determined before breaking the blind
 
 Subjects will be analysed according to randomized treatment.
Safety Set	All randomized participants who take at least 1 dose of study treatment. Participants will be analysed according to randomized treatment.
PK Set	The PK Set will include all participants in the Safety Set who have at least 1 evaluable serum concentration.

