# 4.3 Secondary Efficacy Endpoints

Blood pharmacodynamic markers of neutrophil activation and elastase activity. Change from baseline in the following outcomes at end of the treatment within patient and compared to placebo:

- 1. Plasma desmosine/isodesmosine (only change compared to placebo; withinindividual change is the primary outcome)
- 2. Plasma Aa-Val-360
- 3. Serum NE activity
- 4. Plasma proteinase 3
- 5. Plasma cathepsin B
- 6. Plasma CRP
- 7. Plasma IL-6
- 8. Plasma IL-8
- 9. Plasma IL-1b
- 10. Plasma RANTES
- 11. Plasma LTB4
- 12. Plasma MMP9
- 13. Plasma MMP12
- 14. Plasma MPO
- 15. Plasma PGP
- 16. Plasma PK/PD (LCG/DDS)

The above list was revised from the original protocol as a result of lack of data from sputum and BAL collections due to restrictions during the COVID pandemic. Data on NE may not be available on all subjects.

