# 6 General Aspects for Statistical Analyses

# 6.1 General Methods

Database lock will occur once all subjects complete the final study visit (Safety follow up at Week 16) or terminate early from the study. All analyses will be performed after data lock and cleaning. Statistical analysis will be performed using SAS® version 9.4 or higher. The main population for efficacy analysis will be the Full Analysis Set; supportive analyses will also be performed using the Per-Protocol Set.

Continuous data will be presented using descriptive summaries (e.g., mean, standard deviation, minimum, maximum, median, lower quartile, and upper quartile). Categorical variables will be presented by the number of observations and relative (%) frequency.

Unless otherwise stated, baseline value for any variable will be the last value taken prior to the first dose of study medication. In general, all data will be listed, sorted by site, treatment and subject, and when appropriate by visit number within subject. All summary tables will be structured with a column for Active, Placebo and Total, and will be annotated with the total population size relevant to that table/treatment, including any missing observations.

As a Phase II study, no adjustments for Type I errors (see Section 6.6) will be done. All tests will be 2-sided and conducted at the 5% level. Confidence intervals will be 2-sided 95% confidence intervals.

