# 6.4 Missing Data

Missingness will be assessed and tabulated by treatment group along with reasons for missingness to assess any differential missingness between the treatment arms. Patients impacted by COVID-19 that are related to study discontinuations, missing assessments, and missing visits due to COVID-19 will be created, sorted by patient number, randomized treatment and discontinuation date or visit, as applicable. All data will be listed and sorted by treatment and patient number within treatment.

The efficacy analyses relating to change from baseline will be based on all the available postbaseline measurements. For sensitivity analyses, we will perform a best-case (i.e., replacing missing by best value) and worst-case (i.e., replacing missing with worst value) scenario analyses with respect to the primary outcome and if the results match with the primary analyses, we will stop additional sensitivity analyses.

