# 14 Listing of Tables, Figures, and Listings

# 14.1Listing of Tables

Table	Table Neme	Analysia Cat
Number	Patient Dispesition	Encolled Set
	Prate and Deviations	Enrolled Set
	Protocol Deviations Protocol Deviations Polated to COVID 10	Randomized Set
	Protocol Deviations Related to COVID-19	Ranuomizeu Sei
	Reasons for Exclusion from Analysis Sets	
	Subject Demographic and Baseline Characteristics	Safety Set (SAF)
	Subject Demographic and Baseline Characteristics	Full Analysis Set (FAS)
	Subject Demographic and Baseline Characteristics	Per-Protocol Set (PPS)
	Medical History	Safety Set (SAF)
	Ongoing Medical History	Safety Set (SAF)
	AATD Medical History	Safety Set (SAF)
	Prior Medication	Safety Set (SAF)
	Concomitant Medication	Safety Set (SAF)
	Concomitant COPD Medication	Safety Set (SAF)
	Treatment Compliance	Safety Set (SAF)
	Absolute and Relative Change from Baseline in Plasma	Full Analysis Set (FAS)
	Primary Efficacy Analysis (MMRM)	
	Absolute and Relative Change from Baseline in Plasma Desmosine/Isodesmosine up to End of Treatment: Primary Efficacy Analysis (MMRM)	Per-Protocol Set (PPS)
	Absolute and Relative Change from Baseline in Blood Aα- Val  levels up to End of Treatment: Secondary Efficacy Analysis (MMRM)	Full Analysis Set (FAS)
	Absolute and Relative Change from Baseline in Serum NE activity up to End of Treatment: Secondary Efficacy Analysis (MMRM)	Full Analysis Set (FAS)
	Absolute and Relative Change from Baseline in Plasma proteinase 3 up to End of Treatment: Secondary Efficacy Analysis (MMRM)	Full Analysis Set (FAS)
	Absolute and Relative Change from Baseline in Plasma cathepsin B up to End of Treatment: Secondary Efficacy Analysis (MMRM)	Full Analysis Set (FAS)
	Absolute and Relative Change from Baseline in Plasma CRP up to End of Treatment: Secondary Efficacy Analysis (MMRM)	Full Analysis Set (FAS)
	Absolute and Relative Change from Baseline in Plasma IL- 6 up to End of Treatment: Secondary Efficacy Analysis (MMRM)	Full Analysis Set (FAS)

Table Number	Table Name	Analysis Set
	Absolute and Relative Change from Baseline in Plasma IL-	Full Analysis Set (FAS)
	8 up to End of Treatment: Secondary Efficacy Analysis (MMRM)	, , ,
	Absolute and Relative Change from Baseline in Plasma IL-	Full Analysis Set (FAS)
	1b up to End of Treatment: Secondary Efficacy Analysis (MMRM)	
	Absolute and Relative Change from Baseline in Plasma RANTES up to End of Treatment: Secondary Efficacy	Full Analysis Set (FAS)
	Analysis (MMRM)	

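### The Full Analysis Set requires an evaluable plasma desmosine change but is also used for the other biomarkers and the questionnaires, so some valid data on those endpoints would be excluded unnecessarily

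*SAP*

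**What the plan says.** SAP Section 5, Table 2, sets three conditions for the FAS: randomised, dosed at least once, and "have at least 1 evaluable change from baseline in plasma desmosine / isodesmosine levels". Protocol 10.2 has the same third condition: "have at least 1 evaluable change from baseline in plasma desmosine/isodesmosine levels". Neither document offers a way into the FAS through any other endpoint.

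SAP 6.1 then fixes the populations for all efficacy work: "The main population for efficacy analysis will be the Full Analysis Set; supportive analyses will also be performed using the Per-Protocol Set". The supportive set does not avoid the condition, because "The Per-Protocol Set includes all participants from the Full Analysis Set who have been treated according to the protocol".

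Section 14 applies these sets to endpoints other than DES:

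- The secondary biomarker tables (for example the one whose title reads, in part, "cathepsin B up to End of Treatment: Secondary Efficacy Analysis (MMRM") appear once against the FAS and once against the PPS.
- The listings for SGRQ, SOBQ, MMRC, CAT and pulmonary function are assigned to the FAS.
- The SOBQ and MMRC figures are on the FAS, and the SGRQ figure is on the PPS.

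The Safety Set and PK Set carry no DES condition.

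**The concern.** Whether a participant has a usable DES change is settled after randomisation, and it says nothing about whether their IL-6, Aα-Val360 or CAT result is valid. Read literally, the plan filters on a DES flag before any of the other efficacy models is fitted. A participant with no usable DES baseline, or no usable post-baseline DES value, then leaves all of those analyses, even where the endpoint in question was measured.

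This also runs against the SAP's own stated direction. SAP 10 explains that the primary analysis moved to a mixed model to limit the effect of missing data and use information from all visits, and SAP 6.4 bases change-from-baseline analyses on the measurements available. At stake are some observed values in the secondary and exploratory comparisons. The primary result is not at stake.

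**Working it through.** The plan gives no figure on this point, so the check sets the relevant sections side by side.

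**Step 1. Is there another efficacy population?** SAP Table 2 defines six sets: Enrolled, Randomized, FAS, PPS, Safety and PK. Only the FAS and PPS are assigned to efficacy, and both require a DES change.

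**Step 2. Does any other text create an exception?** SAP 6.4 speaks of available post-baseline measurements but does not say that participants outside the FAS contribute them. SAP 6.1 says biomarkers are summarised on their respective populations but defines no further set. Neither overrides Table 2. Endpoints without a full set of shells fall under the general rule in SAP 6.1: PGP has figures and a listing but no table, and the daily symptom scores have no shell.

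**Step 3. Who would be excluded while holding other valid data?** The visits below come from SAP Table 1 and the Schedule of Activities.

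| Assessment | Visits |
|---|---|
| Plasma DES | 1, 3, 6, 8, 11, 12 |
| Aα-Val360, NE activity | 1, 3, 6, 8, 11, 12 |
| PGP | 1, 3, 11 |
| Proteinase 3, cathepsin B, CRP, IL-6, IL-8, IL-1b, RANTES, LTB4, MMP9, MMP12, MPO | 3, 11 |
| Questionnaires | 3, 6, 11, 12 |

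Each of the other rows is the same as the DES row or a subset of it. (The drug-concentration item listed as PK/PD is also drawn at visits 4, 5 and 9, but concentration summaries use the PK Set.) Three routes to exclusion with other data in hand remain:

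- DES results are missing or not evaluable while other assays or questionnaires succeed.
- Visits yield questionnaires but no blood.
- The participant leaves before Week 4 with diary entries only.

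**Step 4. How much DES must be lost?** After the first dose there are four DES draws (Weeks 4, 8, 12 and 16), three of them inside the Week 12 efficacy window of SAP 8. All must fail. Before the first dose there are two draws, but the SAP is not consistent on whether one can stand in for the other. SAP 6.2 takes the last non-missing pre-dose value, so both must fail. SAP 6.1 fixes biomarker baseline at Study Day 1 pre-dose, and SAP 8 ties baseline to V1. On either of those readings a single failed sample is enough.

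Assume for illustration that each DES sample fails independently with probability q. The chance of exclusion is 1 − (1 − q^b)(1 − q^k), with b = 1 or 2 baseline samples and k = 3 or 4 post-dose samples. For small q this is close to q^b. The size of the problem therefore depends mainly on which baseline rule applies. The documents do not give q.

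**Step 5. Scale per participant.** With 66 planned, 33 per arm, each excluded participant is 1/66 = 1.5% of those randomised, or 1/33 = 3.0% of one arm.

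**The case against.** The strongest reply is that the affected group is nearly empty by design. DES shares its visits with the other biomarkers and the questionnaires, one of several post-dose draws is enough, and SAP 6.1 imputes results outside the quantification limits, so those are not lost. This largely stands and is why the point is small. The exception is the baseline: the second pre-dose sample is a secure fallback only under SAP 6.2.

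Much of the reporting is also already planned. Set membership is fixed before the blind is broken (SAP 5), missingness and its reasons are tabulated by arm (SAP 6.4), exclusions from analysis sets have a table and a listing, and tables carry the relevant population size (SAP 6.1). These steps make the exclusion visible but do not reverse it. A single common set keyed to the primary endpoint is a coherent choice in a signal-seeking study, but nothing in the plan requires the other endpoints to share it.

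A reader might infer more than the documents support in four ways:

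- **That the SAP anticipates selective DES loss.** It does not. "Data on NE may not be available on all subjects" concerns NE, and missing NE removes nobody from the FAS. The reference to "missing assessments, and missing visits due to COVID-19" describes listings, and a missed visit loses the blood sample and the clinic questionnaires together. SAP 10 says spirometry, sputum and BAL became optional, not blood sampling.
- **That early stopping would bias the comparisons through this rule.** SAP 8 uses baseline and Weeks 4, 8 and 12, and the first post-baseline biomarker draw and questionnaire are both at Week 4. Someone who leaves before then has only diary entries, and an endpoint-specific set would omit them from the other endpoints too.
- **That power falls by a stated amount.** Taking the SAP's 82% at 30 per arm implies a standardised difference of 0.755, and 29, 28 or 27 per arm would give 80.7%, 79.2% or 77.7%. But the 82% is power for DES, and the DES analysis loses nothing here, because a participant without a DES change adds nothing to it. The losses of one to three per arm are assumed.
- **That pulmonary function is a leading example.** Shells remain, but SAP 10 says spirometry analyses will no longer be performed.

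**Conclusion.** The point holds as a matter of definition. Followed literally, the SAP discards observed non-DES efficacy data from any participant without an evaluable DES change, and no other section prevents it. The effect is limited to the secondary and exploratory efficacy endpoints other than DES; the DES, safety and PK analyses are untouched. The number affected is unknown and probably small, on the assumption that DES samples fail no more often than others taken at the same visits. It would be larger if baseline rests on a single pre-dose sample. No loss of power or bias can be quantified from the documents. This is an inexpensive improvement of small expected size.

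**What to change.** Restrict the DES condition to analyses of DES. For each other efficacy endpoint, define the set as every randomised participant dosed at least once with a baseline and at least one post-baseline value of that endpoint, analysed in the randomised arm, and show N in each table.

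Align protocol 10.2, the PPS definition in SAP Table 2 and the set labels in SAP Section 14, and record the change in SAP 10. Do this before the blind is broken, as SAP 5 already requires for deciding set membership.

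The cost is minor editing, one population flag per endpoint, and an N that varies between tables. The change removes an unnecessary exclusion. It does not remove bias from missing values of the endpoint itself, because the new set also depends on post-randomisation availability of that endpoint.

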# 6 General Aspects for Statistical Analyses

# 6.1 General Methods

Database lock will occur once all subjects complete the final study visit (Safety follow up at Week 16) or terminate early from the study. All analyses will be performed after data lock and cleaning. Statistical analysis will be performed using SAS® version 9.4 or higher. The main population for efficacy analysis will be the Full Analysis Set; supportive analyses will also be performed using the Per-Protocol Set.

Continuous data will be presented using descriptive summaries (e.g., mean, standard deviation, minimum, maximum, median, lower quartile, and upper quartile). Categorical variables will be presented by the number of observations and relative (%) frequency.

Unless otherwise stated, baseline value for any variable will be the last value taken prior to the first dose of study medication. In general, all data will be listed, sorted by site, treatment and subject, and when appropriate by visit number within subject. All summary tables will be structured with a column for Active, Placebo and Total, and will be annotated with the total population size relevant to that table/treatment, including any missing observations.

As a Phase II study, no adjustments for Type I errors (see Section 6.6) will be done. All tests will be 2-sided and conducted at the 5% level. Confidence intervals will be 2-sided 95% confidence intervals.

Biomarker data are reported as concentration results, measured using a specific assay with a working range defined by the two limits: Lower limit of quantification (LLOQ) and Upper limit of quantification (ULOQ). Values which fall below the LLOQ or above the ULOQ are reported as <LLOQ \* dilution factor (dilution factor: if sample diluted and concentration measured still below LLOQ) and > ULOQ \* dilution factor, respectively. All results for the above biomarker parameters, if collected, will be summarised on the respective populations by descriptive statistics stratified by treatment and time-point, and including the geometric mean and coefficient of variation. Changes in the biomarker concentrations from baseline (Study Day 1 pre-dose) will be also summarised at each post-baseline time-point. In the summary table, the frequency (n, %) of values below the LLOQ and above the ULOQ, respectively, will be included. In case of values below the LLOQ and/or values above the ULOQ, the values, reported as <LLOQ will be imputed as 0.5\*LLOQ and values reported as >ULOQ will be imputed as 1.5\*ULOQ.

# 6.2 Key Definitions

	57
Terminology	Definition
Baseline value	defined as the last non-missing value prior to first study treatment dose
End of Treatment (EOT) Visit	visit refers to the final day of study treatment administration including cases of premature discontinuation of the study treatment.
End of Treatment (EOT) Value	Last non-missing post-baseline value under study treatment.
Treatment Period	duration that a subject is under treatment in the study between the date of first study treatment intake and the date of last study treatment intake.
Study duration (in days), time to day of last visit or the day of study termination	Calculated as: Date of Safety follow-up (FU) visit (or EOT visit in case of premature discontinuation) – Date of Baseline (Day 0) + 1.
Study Completion and Withdrawal	
 
A subject will be defined as "completed the study" if subject completes the follow-up at Week 16 – either having completed, all or partially, the protocol defined visits before Week 16.
 
Termination/withdrawal at a different time point will be considered as study discontinuation/withdrawal.
 

EndPoint value	considered the value at Week 12 or EOT value (last non-missing post-baseline value under treatment)
Relative change from baseline	defined as percentage change from baseline Calculated as: [(Post-baseline value – Value at baseline)/ Value at baseline]x100%

### Table 3: Definitions of Terminology

Absolute change from baseline	Calculated as: Absolute change = Post-baseline value – Value at baseline
Efficacy Offset Period	Change from Week 12 to end of study follow-up at Week 16

# 6.3 Covariates and Subgroups

Prespecified covariates have been provided in the above efficacy analyses. Covariates to be included in the primary and secondary efficacy analyses on change in the biomarkers are baseline values, age and smoking history. Although we have stratified randomization by genotype, we will not include genotype as a covariate in the main analyses. Depending on available data, we may be able to compare outcomes between genotypes, but this will be exploratory in nature.

Due to the change in protocol to drop augmentation therapy from the exclusion criterion, subgroup analyses between those enrolled with and without augmentation will be performed as secondary analyses.

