### **3.2. Study Rationale**

The aims of this study are to build on the previous alvelestat (MPH966) clinical experience and to confirm mechanistic efficacy through elastase inhibition in the AATD population and investigate the safety and tolerability of alvelestat (MPH966) in the target population. Clinical efficacy endpoint studies in AATD-related lung disease often involve longer-term studies and are therefore inappropriate for decision making at the early stages of clinical development. The availability of biomarkers of elastolysis, which have been investigated in AATD, correlate with lung damage, and show treatment response over periods of 4 to 12 weeks, enables a study design to demonstrate mechanistic effects over an appropriate time period for a proof-of-concept trial. Greater efficacy and clinical benefit is expected by targeting patients with AATD-related lung disease, in which neutrophil elastase is considered the key pathogenic driver, and by using a dose of alvelestat (MPH966) to maintain neutrophil elastase inhibition throughout the 24-hour period.

Biomarkers of inflammation and lung matrix breakdown will be used to provide evidence that the inhibitory effect of alvelestat (MPH966) on neutrophil elastase may deliver potential clinical benefit demonstrated by effects on the pathogenic progresses that drive disease progression. This potential will be tested in patients receiving augmentation, which is the standard of care in many countries, as well as in those not receiving augmentation. These efficacy data in combination with safety and tolerability will be used to make progression decisions on alvelestat (MPH966) development in AATD.

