# 3.5.3 Sample Size

Over the course of the study, target enrolment is 66 with the goal of 60 completers. Participants will be randomized in a 1:1 ratio to receive one of the following: 120mg Alvelestat (MPH966) BID or placebo. Randomization will be stratified by AAT genotype/phenotype.

The study will be powered for within-individual change in plasma desmosine/isodesmosine (DES) as the primary endpoint at Week 12 compared to baseline. A sample size of 30 participants in the MPH966 treatment group will give us >90% power to detect a 15% mean decrease of plasma DES from baseline to 12 weeks follow-up in patients treated with MPH966 (within subject change) using a two-sided paired t-test at  $\alpha$ =0.05. The calculation is based on an assumed correlation value of 0.5, baseline mean DES value of 0.466 and standard deviation of 0.09. This 15% mean decrease has been observed in trials of standard dose augmentation versus placebo (Ma S, 2013). A recent study of double dose versus single dose augmentation revealed a within subject decrease in plasma DES from 0.42 +/-0.03 ng/ml to 0.38 +/- 0.03 ng/ml (Campos MA, 2019). We will have >99% power to detect a comparable difference in DES in those who have Alvelestat added to augmentation if we assume their observed SD=0.03 and 85% power if we double their assumed SD, i.e., SD=0.06. Power will not be enough (~50%) to detect this difference if we use our original SD value of 0.9.

For comparing the mean change in DES between the two groups (placebo vs. MPH966), and assuming that there is no placebo effect over 12 weeks, a two-sided two sample t-test at  $\alpha$ =0.05 with a sample size of 60 (30 per group) reveals that we will have 82% power to detect a 15% difference in mean change in plasma DES.

By including a 10% attrition rate over 12 weeks, the required sample size is inflated to 66 (33 per group) to achieve the estimated powers. If we observe attrition rate less than we expected, we will have more statistical power to detect the expected differences. As one interim analysis will be conducted only for safety concerns (see Data Safety and Monitoring Plan), no adjustments to the Type I error are considered for estimating statistical powers.

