# 10 Changes from Analysis Planned in the Protocol

In Version 1.3 of the protocol, augmentation therapy was removed from the list of not allowed treatment. Sample size calculation was revised but sample size remained the same. Also, stratified analyses by augmentation therapy will be performed.

Due to the risk during the COVID pandemic, spirometry as well as sputum and BAL collections were changed to optional. Consequently, all analyses using spirometry, sputum biomarkers, and BAL biomarker outcomes and data will no longer be performed in this study.

Primary analysis in the protocol is based on ANCOVA with outcome being the percent change at Week 12 from baseline. However, to minimize the effect of missing data and to maximize the information from all visits, the primary analysis is now based on fitting a mixed model using change from baseline at all available follow-up visits as outcome with the assumption of missing at random for missing data.

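### The SAP plans secondary analyses by augmentation status but specifies no treatment-by-augmentation contrast, so no planned output shows whether the drug effect differs between the two groups

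*SAP*

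**What the plan says.** Protocol 3.2 makes augmentation part of the rationale: "This potential will be tested in patients receiving augmentation, which is the standard of care in many countries", alongside patients not receiving it. SAP 6.3 commits to an analysis: "subgroup analyses between those enrolled with and without augmentation will be performed as secondary analyses". SAP 10, listing changes from the protocol, says that "stratified analyses by augmentation therapy will be performed". SAP 6.1 sets the test level: "All tests will be 2-sided and conducted at the 5% level". SAP 6.6 makes no multiplicity adjustment.

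No model is written for the augmentation analyses. The two efficacy models that are written treat augmentation as follows:

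- **SAP 8.1 (primary, within arm).** The code runs by treatment arm. AUGMENTATION is a main effect, and the only means requested are those by visit.
- **SAP 8.2 (between arms).** The model has treatment, visit and their interaction, with baseline, FEV1, age and smoking. It has no augmentation term. A between-arm p-value below 0.05 is read as a treatment effect for that outcome.

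The list of tables in SAP 14.1 contains no comparison of the drug effect by augmentation status. Randomization in SAP 3.5.3 is stratified by genotype, not by augmentation, and neither document gives the expected split.

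**The concern.** Whether the drug effect differs with augmentation is a question about a difference between two effects. Separate analyses in two small strata do not answer it: with modest power in each, one can cross p<0.05 and the other miss it although the true effects are equal. The only decision rule that the SAP writes for a between-arm comparison is p<0.05. A reader given two stratum tables and no contrast has little else to go on.

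Protocol 3.2 says the efficacy data will inform decisions on further development, so a spurious contrast between the groups would matter.

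**Working it through.** **Inputs**

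- Baseline mean, SD and correlation (SAP 3.5.3): "assumed correlation value of 0.5, baseline mean DES value of 0.466 and standard deviation of 0.09". The SD of change is 0.09 × √(2 × (1 − 0.5)) = 0.09. I take the unit as ng/ml, as for the cited study in the same section.
- Effect: 15% of 0.466 = 0.0699.
- Two-sided 5% tests and 1:1 allocation, with 30 completers per arm (SAP 3.5.3, 6.1).
- Assumed: the augmentation split, taken as 15/15 per arm with a range to 6/24, and arms balanced within strata.

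Unadjusted t-tests stand in for the mixed models, as in the SAP's own power calculation.

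**Reproducing the plan's figures**

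- Paired test, n = 30: noncentrality 0.0699 / (0.09/√30) = 4.25, power 98.4%. This agrees with ">90% power to detect a 15% mean decrease of plasma DES from baseline to 12 weeks follow-up".
- Two-sample test, 30 per arm: noncentrality 0.0699 / (0.09 × √(2/30)) = 3.01, power 84.1%. The SAP "reveals that we will have 82% power to detect a 15% difference in mean change in plasma DES". An SD rounded from 19.3% to 20% of the mean gives 81.5%, so rounding is a plausible explanation. Calibrating the effect to exactly 82% changes the 15/15 between-arm result below only from 49.7% to 50.0%.

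**Identical true effect in both strata**

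With stratum powers p1 and p2, the chance that exactly one stratum is significant is p1(1 − p2) + p2(1 − p1).

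- Between arms, 15 per arm per stratum: noncentrality 0.0699 / (0.09 × √(2/15)) = 2.13, power 53.7%. Exactly one significant: 2 × 0.537 × 0.463 = 49.7%. Both are significant in 28.9% and neither in 21.4%.
- Within the active arm, n = 15 per stratum: noncentrality 0.0699 / (0.09/√15) = 3.01, power 79.9%. Exactly one significant: 2 × 0.799 × 0.201 ≈ 32%.

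| Split per arm | Between arms: powers | Exactly one significant | Within active arm: powers | Exactly one significant |
|---|---|---|---|---|
| 15/15 | 53.7%, 53.7% | 49.7% | 79.9%, 79.9% | 32.2% |
| 12/18 | 44.4%, 61.9% | 51.3% | 68.8%, 87.4% | 35.9% |
| 10/20 | 37.6%, 66.8% | 54.2% | 59.1%, 90.9% | 42.6% |
| 8/22 | 30.5%, 71.1% | 58.3% | 47.4%, 93.5% | 52.3% |
| 6/24 | 23.0%, 75.0% | 63.5% | 33.9%, 95.4% | 64.6% |

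A simulation of 40,000 trials gave 49.8% (between) and 32.1% (within) at 15/15. In the same simulated data a treatment-by-augmentation test declared a difference in 4.9% of trials at 15/15 and 5.0% at 8/22 and 6/24.

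**Sensitivity at 15/15**

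- A correlation of 0.3 gives 48% between arms and 45% within; 0.7 gives 37% and 9.5%.
- SAP 3.5.3 also considers a change of 0.04 (0.42 to 0.38) in augmented patients. If both strata had that effect, the figures are 11% and 0.5% at SD 0.03, 49% and 44% at SD 0.06, and 34% and 46% at SD 0.09 (printed there as 0.9, which I read as a slip).

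**What an interaction model would show**

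At 15/15 the standard error of the difference between the two effects is 0.09 × √(4/15) = 0.0465. With 56 degrees of freedom the 95% half-width is 2.003 × 0.0465 = 0.093, or 0.093/0.466 = 20% of baseline. If the drug had the full 15% effect in one stratum and none in the other, the interaction test would have about 31% power.

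**The case against.** The documents can be read more kindly, and much of that reading stands.

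- **The wording in 6.3 may mean a direct comparison of the two groups.** It may. But SAP 10 says stratified, and no model settles it.
- **Protocol 3.2 asks about an effect in each group, not a contrast, and no listed objective asks whether the effects differ.** This is correct, and stratum-specific estimates would answer that question. They do not protect a reader who sets the two side by side.
- **The primary model run by arm does yield an augmentation coefficient in each arm, and the difference between those coefficients is a form of the contrast, averaged over visits.** This is also correct. The SAP does not say that either coefficient or their difference will be reported, and the 8.2 model offers nothing equivalent.
- **The size depends on an unstated split and on the SD.** It does. A small SD in augmented patients would shrink it sharply.
- **These are secondary, unadjusted analyses in a trial the SAP describes as signal-seeking, and an interaction test would have little power.** Both are true. They limit the weight of the point and argue for an estimate with its CI over a test.

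A reader might go further and infer that the SAP will declare a difference whenever one stratum is significant and the other is not, or that phase 3 eligibility would follow from it. The documents support neither. The p<0.05 rule in 8.2 concerns the treatment effect for each outcome, not a difference between subgroups, and no section ties later eligibility to augmentation status.

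**Conclusion.** The gap is real: the SAP commits to analyses by augmentation status and specifies no treatment-by-augmentation contrast in any model or listed table. If the strata are analysed separately and judged by p<0.05, equal true effects would be significant in only one stratum in about 50% of trials between arms and about 32% within the active arm. These figures rest on the SAP's effect and SD of 0.09 in both strata and on an assumed even split. Less even splits raise both, to about 65% at 6/24.

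These figures do not mean that half of trials would lead the sponsor to claim a difference, because the SAP states no such rule. The primary conclusion is unaffected. The point is worth acting on because a better-suited analysis is available from data already being collected.

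**What to change.** In SAP 6.3, 8.2 and 10, specify one model with both arms and all participants, adding AUGMENTATION and TRTP*AUGMENTATION to the 8.2 terms. Add the interactions with AVISIT only for markers with more than one post-baseline visit; most secondary markers in SAP Table 1 are measured only at Visits 3 and 11, so need none.

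Report the Week 12 treatment effect in each augmentation group and the difference between the two effects with its 95% CI, all from that model. State that any claim of a differing effect rests on that CI and is a secondary, signal-seeking estimate.

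The cost is a few sentences, one further model statement and a table. Augmentation status at enrolment is already recorded and used in 8.1, so no new data are needed. The drawback is that the wide interval will usually leave the question open.
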